5.1 Adverse Events

An adverse event (AE) is any unfavorable and unintended sign, symptom, or disease temporally associated with the use of a medicinal product, whether or not considered related to the treatment.

Each subject will be monitored for the occurrence of AEs, including SAEs, immediately after treatment initiation. At each visit, the investigator or other site staff will question the Subject about adverse events using an open question taking care not to influence the Subject's answers (e.g., "Have you had any medical problems since your last visit?").

Any adverse event, whether or not it is related to the treatment procedure, will be reported on the Adverse Event form along with the date of onset, the severity, the relationship to the treatment, and the outcome. Under certain circumstances, additional information may be requested.

When an adverse event persists at the end of the study, the Investigator will ensure a follow-up of the Subject until the Investigator agrees the event is satisfactorily resolved or no further follow-up is required. The study requires that Subjects be actively monitored for adverse events up to and including 14 days after last day of the study.

The severity of an adverse event will be scored according to the following scale:

Score _____ Interpretation _____

CONFIDENTIAL

1	Mild	Awareness of sign or symptom, but easily tolerated
2	Moderate	Discomfort enough to cause interference with usual activity
3	Severe	Incapacitation with inability to perform usual activity

The relationship of an adverse event to RenewalNail™ plasma treatment is to be assessed according to the following definitions:

Not related – no temporal association, or the cause of the event has been identified, or the RenewalNail™ plasma treatment cannot be implicated based upon available information.

Possibly related – temporal association, but other etiologies are likely to be the cause. However, involvement of the RenewalNail™ plasma treatment cannot be excluded, based upon available information.

Probably related – temporal association, other etiologies are possible, but unlikely, based upon available information.

Related – established temporal or other association to the event is not reasonably explained by the Subject's known clinical state or any other factor, based on available information.

5.2 Serious Adverse Events

A serious adverse event (SAE) or reaction is defined as any untoward medical occurrence that at any dose:

- results in death;
- is life-threatening, (the term “life-threatening” in the definition of “serious” refers to an event in which the Subject was at risk of death at the time of the event; it does not refer to an event which hypothetically might have caused death if it were more severe);
- requires inpatient hospitalization or prolongation of existing hospitalization;
- results in persistent or significant disability/incapacity; or
- is a congenital anomaly/birth defect.

Any SAE occurring in a Subject receiving study solution, and any SAE occurring during the 30 days post-treatment that the Investigator becomes aware of, must and will be reported by the Investigator or designee to the Study Medical Monitor within 24 hours even if the SAE does not appear to be RenewalNail™ plasma treatment related. This should be done by telephone and by sending a copy of the Serious Adverse Event form plus other supporting documentation, as required.

All additional follow-up evaluations must be reported to the Sponsor immediately. All SAEs will be followed until the Investigator/Sponsor agrees the event is satisfactorily resolved or no further follow-up is required.

The Investigator/Sponsor will be responsible for notifying the relevant authorities of any SAE, as outlined in the ICH Guidelines. The Sponsor will also ensure that the appropriate IRB is notified of the SAE.

5.3 Risk Management

Subjects will be followed closely during the course of the trial and will have access to the Investigator and/or study staff at all times via provision of after-hours telephone. All known risks will be disclosed to

CONFIDENTIAL

the Subject via the informed consent process. Subjects will be informed both verbally and in writing in a timely manner of any new information that might relate to safety or their willingness to continue in the study.

6.0 BENEFITS

There is no guarantee of success for the treatment. To the extent that a Subject may be uncertain if they have a fungal nail infection, the screening in this study may provide them with a laboratory result that positively or negatively supports this diagnosis. Being in this study may reduce or eliminate their fungal nail infection, but this is an experimental study and there is limited information about the safety and effectiveness of plasma treatment for fungal nail infections.

There may be a societal benefit from what is learned leading to improved onychomycosis treatment in the future.

7.0 Test Materials

7.1 Administration

Device Name	RenewalNail™ Treatment System DFPD-003
Treatment Schedule	45-minute treatments on Study Visits 1, 2 and 3
Route of Administration	Topical

7.2. Packaging and Labeling

Study Device (RenewalNail™ plasma treatment device) will be packaged to ensure safe transportation from the Sponsor's site to the study site. Each Device and Disposable will be labeled with a unique ID number for tracking purposes. *Instructions for Use* and warnings will be included.

Study Device label will include the Sponsor's name, study protocol number, and warning: "Caution: Limited by Federal (United States) law to investigational use only."

7.3 Subject Treatment and Use Instructions

Each Subject receiving treatment will receive verbal instructions as part of the informed consent regarding the treatment protocol. All site personnel taking part in the study will be trained on handling and use of the device. Each Subject's plasma gas treatment will be done automatically and under the supervision of the Investigator.

7.4 Accountability

The Sponsor will provide the study Device, Disposables, Nail Penetration Enhancer (perfluorodecalin), and *Instructions for Use* documents to the Investigator. Receipt of all study supplies will be confirmed and documented by the site. In accordance with federal regulations, the Investigator must agree to keep all clinical supplies in a secure location with restricted access. All supplies provided to the Investigator must not be used in any unauthorized manner. All used and unused supplies will be appropriately inventoried and returned to the Sponsor.

CONFIDENTIAL

7.5 Prior and Concomitant Therapy

Therapies used within six months of signing the Informed Consent Form should be recorded on the Previous/Concomitant Therapy Form of the CRF. Washout medications should be listed on the Previous/Concomitant Therapy Form when applicable.

Information on concomitant therapy should be recorded on the Previous/Concomitant Therapy Form of the CRF. Any therapy used by the Subject will be considered concomitant therapy (e.g., antifungal therapy, birth control pills, immunosuppressant therapy, etc.). Every attempt should be made to keep concomitant therapy dosing constant during the study. Any change to concomitant therapy should be noted on the Previous/Concomitant Therapy Form. An Adverse Event Form should be completed for any Subject starting a concomitant therapy (except therapies used prophylactically) to treat any health condition/event not identified in the Subject's baseline medical history.

8.0 Monitoring

8.1 Clinical Monitoring/Auditing

The Sponsor will ensure that a qualified monitor is available to oversee the conduct of the trial and that monitoring is performed in accordance with applicable procedures and regulations. The monitor will evaluate compliance with the investigational plan, FDA regulations, IRB guidelines, and the signed Investigator agreement. In addition, inspections or on-site audits may be carried out by the FDA or by the Sponsor's independent Quality Assurance Department. The Investigator will allow the Sponsor's representatives and any regulatory agency to examine all study records, CRFs, corresponding Subject medical records, and any other documents considered source documentation. The Investigator will allow a representative of the Sponsor to observe the treatment as part of a technical assessment about the performance of the instrument, as long as the Subjects have provided optional consent for this observation. The Investigator also agrees to assist the representative, if required.

8.2 Regulatory Obligations

The RenewalNail™ plasma treatment device is a Non-Significant Risk Investigational Device and as such is Subject to the abbreviated IDE regulations, including records and reporting, device disposition, and study monitoring.

9.0 Statistical Methods Planned

Due to the nature of the study and the small number of Subjects, no inferential statistical analyses will be performed. The results from this study will be used to determine whether the treatment can achieve mycological cure for onychomycosis Subjects fulfilling the inclusion/exclusion criteria.

Mycological cure is defined as an achievement of negative culture results for both *Trichophyton rubrum* and *Trichophyton mentagrophytes* from both Visit 3 and Visit 4.

The data is too small to summarize with descriptive statistics; therefore, Subject listings will be presented.

CONFIDENTIAL

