by *Trichophyton rubrum* or *Trichophyton mentagrophytes*.

SPONSOR: DeviceFarm, Inc.
[name]
[name]

Approvals	Signature	Date
[name] CEO DeviceFarm, Inc.		

CONFIDENTIAL

SYNOPSIS

Title of Study:

A Single Center Open Label Early Feasibility Study to Evaluate the Efficacy and Safety of the RenewalNail™ Plasma Treatment System in Patients with Mild to Moderate Onychomycosis (Fungal Nail) of the Hallux caused by *Trichophyton rubrum* or *Trichophyton mentagrophytes*.

Objective:

To determine if a three-treatment protocol with the RenewalNail™ plasma treatment system over a week will result in mycological cure and/or clear nail growth on the treated hallux toe.

Methodology:

Single-center, open-label

Number of Subjects (planned):

5 Subjects

Number of Sites and Number of Subjects Per Site:

One (1) site, 5 Subjects

Diagnosis and Main Criteria for Inclusion:

Laboratory confirmed diagnosis of mild to moderate onychomycosis on at least one hallux toe caused by *Trichophyton rubrum* or *Trichophyton mentagrophytes*

Male and female Subjects of any race between 21 and 75 years of age meeting specific inclusion/exclusion criteria

Investigational Product:

RenewalNail™ Plasma Treatment System (DFPD-003)

Mode of Administration: topical

Number of treatments: 3

Duration of each treatment: 45 minutes

Criteria for Evaluation:**Efficacy:**

Mycological Cure: Two consecutive negative mycology cultures

Clinical Cure: Photographic evidence of clear nail growth

Safety:

Adverse Events

STUDY CONTACTS

SPONSOR/SITE PERSONNEL		
Name/Title	Affiliation/Address/Tel.	Responsibilities
[name] CEO	DeviceFarm Inc. [name] [name] [contact]	Sponsor Contact
[name] VP of Operations	DeviceFarm Inc. [name] [name] [contact]	Sponsor Contact
[name] Acting Head of Clinical Operations	DeviceFarm Inc. [name] [name] [contact]	Sponsor Contact/ Study Monitor
[name]	[name] [name] [contact] [contact] [name]	Principal Investigator

CONFIDENTIAL

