2.0 STUDY OBJECTIVES

The purpose of this study is to assess the clinical feasibility of DeviceFarm, Inc.'s RenewalNail™ system and the treatment protocol that was developed based on extensive laboratory testing on human cadaver nails.

The primary objective of this study is to evaluate the efficacy and safety of the RenewalNail™ plasma treatment system and Protocol in achieving mycological cure for the patient. The Protocol calls for three 45-minute treatments performed over a week to achieve mycological cure. Mycological cure will be assessed with two consecutive mycological culture tests done over a week. Two consecutive negative mycology culture results confirm the elimination of fungus causing onychomycosis infection, as recommended by recent FDA guidance. There will be no placebo arm in the study.

Secondary objectives include:

- Will the treatment protocol result in clear nail growth for the patient over a 5-month interval?
- Is the instrument functional in a clinical setting as related to user instructions, user interface and human factor analysis?
- Are there treatment protocol or instrument changes that would improve the treatment results, patient safety, or patient comfort?
- Are there fungal species beyond *Trichophyton rubrum* and *Trichophyton mentagrophytes* that are not affected by the treatment, as seen in species identification from the nail scrapings?

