3.2 Discussion of Study Design

This study will be conducted as a Single-center, open-label, pilot study involving 5 Subjects. After giving informed consent, each Subject will be screened for eligibility according to inclusion/exclusion criteria. A Subject will be considered evaluable if he or she satisfies all admission criteria for entry into the study and completes the treatment protocol.

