9.1 Safety Analyses

The type, severity, duration, and frequency of reported adverse events will be tabulated. Adverse events will also be summarized for events that were considered treatment-related. Adverse events will be presented in Subject listings to include the start date and time, stop date and time, relationship to study procedure, severity, and action taken. Serious adverse events will be presented in a separate listing. The safety endpoints will be an assessment of:

- Device-related adverse events
- Overall rate and severity of all reported adverse events

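### Section 9.0 plans a yes/no conclusion on mycological cure from five subjects, with no number of cures that counts, no efficacy summary and no statement of imprecision

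*Protocol*

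**What the plan says.** The Protocol describes a small uncontrolled study. Section 3.2: "This study will be conducted as a Single-center, open-label, pilot study involving 5 Subjects". Section 2.0: "There will be no placebo arm in the study".

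Section 9.0 makes three statements that have to be read together:

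- On inference: "no inferential statistical analyses will be performed", with the nature of the study and its size given as reasons.
- On use of the results: they will be "used to determine whether the treatment can achieve mycological cure for onychomycosis Subjects" who meet the entry criteria.
- On description: "The data is too small to summarize with descriptive statistics", so that only listings by subject are planned.

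The Synopsis words the objective in the same yes/no form: "To determine if a three-treatment protocol with the RenewalNail™ plasma treatment system over a week will result in mycological cure" (it goes on to add clear nail growth). Section 2.0 makes efficacy in achieving mycological cure part of the primary objective.

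Cure is defined for the individual subject (Sections 4.2 and 9.0): negative cultures at both Visit 3 and Visit 4. No section says how many subjects must meet that definition for the study's answer to be positive.

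For safety, Section 9.1 plans tabulations, and one of its two endpoints is "Overall rate and severity of all reported adverse events".

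**The concern.** The conclusion in Section 9.0 is about a class of patients, those who meet the entry criteria, and it is yes or no. The output planned to support it is a listing, with neither a proportion nor a measure of precision. Because no number of cures is fixed, the smallest number compatible with the wording is one.

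This is not a matter left to an SAP. The Protocol itself excludes the efficacy summary, so an SAP that added one would contradict it.

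The stated reason, too few data, is also not applied evenly. If these subjects can carry an adverse event rate, they can carry a count of cures over a denominator.

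At stake is how the result is read. A bare statement that the treatment can achieve cure could be taken as a demonstration of efficacy when the data are compatible with a very wide range of cure rates. An uncured subject whose two cultures were falsely negative would also count as a cure.

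**Working it through.** **Inputs.** Planned n = 5, single arm (Synopsis, Sections 3.1 and 3.2). Success per subject is two negative cultures (Sections 4.2 and 9.0). The Protocol gives no alpha, target rate or success threshold and no derivation of n = 5, so it has no figure of its own to reproduce.

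**Step 1: precision of x cures in 5.** The exact (Clopper-Pearson) 95% limits are the 2.5% quantile of Beta(x, 6 − x) and the 97.5% quantile of Beta(x + 1, 5 − x). Three limits can be checked by hand:

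- 5/5 lower limit: 0.025^(1/5) = 0.478
- 0/5 upper limit: 1 − 0.025^(1/5) = 0.522
- 1/5 lower limit: 1 − 0.975^(1/5) = 0.005

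| Cured | Proportion | Exact 95% interval |
|---|---|---|
| 0/5 | 0% | 0 to 52.2% |
| 1/5 | 20% | 0.5 to 71.6% |
| 2/5 | 40% | 5.3 to 85.3% |
| 3/5 | 60% | 14.7 to 94.7% |
| 4/5 | 80% | 28.4 to 99.5% |
| 5/5 | 100% | 47.8 to 100% |

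Even the best possible result leaves a true double-negative rate just under one half compatible with the data. The worst leaves a rate just over one half compatible.

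**Step 2: how easily one double-negative subject arises.** If p is the true double-negative rate, P(at least 1 of 5) = 1 − (1 − p)^5. Section 1.0 quotes cure rates of 5 to 17% for topical therapy. Putting these in for scale only gives 1 − 0.95^5 = 22.6% and 1 − 0.83^5 = 60.6%. The Protocol does not set these rates as a benchmark, and they may refer to a different endpoint.

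**Step 3: illustration for an ineffective treatment.** The documents give no false-negative rate for a culture. Assume a rate f per culture and independence of a subject's two cultures, so that p = f²:

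| Assumed f | f² | P(at least 1 of 5) = 1 − (1 − f²)^5 |
|---|---|---|
| 0.1 | 0.01 | 4.9% |
| 0.2 | 0.04 | 18.5% |
| 0.3 | 0.09 | 37.6% |
| 0.5 | 0.25 | 76.3% |

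If the two cultures were fully correlated, p = f and the figure at f = 0.1 rises to 1 − 0.9^5 = 41.0%.

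**Step 4: the denominator.** Section 3.2 calls a subject evaluable only on completing treatment. Section 3.4.1.4 plans to replace subjects who drop out before completing the three treatments. With one such replacement, six subjects are treated and five complete. Three cures would then be 3/5 = 60% of completers but 3/6 = 50% of those treated. The intervals in step 1 apply only if the denominator is five.

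**The case against.** This is an early feasibility study. The sentence at issue speaks of what the treatment can do, next to an explicit refusal of inference, so it is closer to proof of concept than to a claimed cure rate. Declining hypothesis tests with five subjects is sensible. A listing of about five subjects shows every outcome, and any reader can count the cures and work out an interval. Adverse events can recur within a subject, so tabulating them is ordinary safety reporting and only a partial parallel. An interval such as 15% to 95% mostly restates that n is five. It does nothing about misclassified cultures or the missing control: if false negatives produced 5/5, an interval of 48% to 100% would look like stronger evidence.

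Much of this stands, and it limits the point in four ways.

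- A reader might infer that one cure would settle the matter. The Protocol sets no threshold, so it only could.
- A reader might infer that the uncertainty is hidden. It can be recovered from the listing, but it is not part of the planned output and does not temper the planned conclusion.
- A reader might take the step 3 probabilities as this trial's false-positive risk. They rest on an assumed f. Section 3.3.1 requires a positive KOH test and a positive culture at entry, which may make high values of f less plausible.
- A reader might think an interval cures the problem of false negatives. It does not, and the report must say so.

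What the objection does not answer is that Section 9.0 announces a determination about a patient class, excludes the simplest summary that would support it, and gives a reason that Section 9.1 does not follow.

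**Conclusion.** The point holds as a modest reporting and wording defect. Section 9.0 pairs a yes/no conclusion with no criterion and no efficacy summary, so a single double-negative subject could be offered as a positive answer without its imprecision being shown. That imprecision is large: 0.5% to 72% for 1/5, and 48% to 100% even for 5/5.

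The intervals assume n = 5 and independent subjects, and need nothing else from outside the Protocol. The chance of at least one apparent cure from an ineffective treatment, about 5% at f = 0.1 to 76% at f = 0.5, is an illustration under an assumed rate and independent cultures, not an estimate for this trial. The documents do not support a claim that omitting hypothesis tests is wrong, or that a positive conclusion from one cure is what the sponsor intends.

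**What to change.** In Section 9.0:

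- Keep the subject listings.
- Add the number with mycological cure over all subjects treated, including any who drop out and are replaced, with an exact Clopper-Pearson 95% interval. A treated subject without negative cultures at both Visit 3 and Visit 4 has not met the definition and counts as not cured.
- If the two denominators differ, show the count among evaluable completers (Section 3.2) beside it.
- Replace the sentence on use of the results with one that describes the outcome as a descriptive feasibility estimate with that interval. No threshold is then needed.
- State that the interval reflects sampling error only and does not account for false-negative cultures or the absence of a control arm.
- Remove the statement that the data are too few to describe. Narrow the exclusion of inferential analysis to hypothesis tests, since a confidence interval is itself inferential.

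The cost is one line of analysis and a few changed sentences, with no new data and no change to study procedures. The downside for the sponsor is a result that looks less certain than a plain statement of cure.

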9.1 Safety Analyses

The type, severity, duration, and frequency of reported adverse events will be tabulated. Adverse events will also be summarized for events that were considered treatment-related. Adverse events will be presented in Subject listings to include the start date and time, stop date and time, relationship to study procedure, severity, and action taken. Serious adverse events will be presented in a separate listing. The safety endpoints will be an assessment of:

- Device-related adverse events
- Overall rate and severity of all reported adverse events

9.2 Changes in Study Conduct/Statistical Analyses /Amendments

No change in the conduct of the study should be instituted without written approval from the Sponsor and the IRB.

10.0 ETHICS AND GENERAL STUDY CONDUCT CONSIDERATIONS

10.1 Institutional Review Board (IRB)

This study and all appropriate amendments will be reviewed and approved by an Institutional Review Board according to the established IRB procedures.

10.2 Ethical Conduct of the Study

This study will be conducted in accordance with the ethical principles originating from the Declaration of Helsinki and GCPs.

10.2.1 Principal Investigator

The Principal Investigator is responsible for conducting this study in accordance with all applicable laws and IRB approved documents. The Investigator must ensure adherence to the procedures outlined in this Study Protocol. The procedures set out in this study protocol, pertaining to the conduct, evaluation, and documentation of this study, are designed to ensure that the Investigator abides by GCP as described in the ICH Guidelines Topic E6: "Guideline for Good Clinical Practice." Compliance with these regulations also constitutes compliance with the ethical principles described in the current revision of the Declaration of Helsinki. The study will also be carried out in keeping with local legal and regulatory requirements.

